7.1.3.2 Breast Screening Programme Invitation

Patients should be advised to contact the Research Team at their randomising hospital if they receive an invitation to attend for a mammogram through the NHS Breast Screening Programme during trial participation. Patients do not need to attend these additional appointments.

7.1.4 Investigations and Treatment of Ipsilateral Breast Disease

Investigations and treatment of ipsilateral breast disease in the Surgery arm patients will be in accordance with local protocol.

7.1.5 Investigations and Treatment of Contralateral Breast Disease

Suspected new disease in the contralateral breast should be investigated and treated according to local protocol. Details of confirmed disease in the contralateral breast will be collected on the CRF.

7.1.6 Data Capture

Data on the outcome of annual mammography, all related investigations (regardless of outcome) and treatment, related referrals to other healthcare practitioners and development of new breast disease will be collected annually on the CRF.

Further details on the progression of disease, development of new breast disease and development of first related distant metastases will be reported on the appropriate CRF.

7.1.7 Related Adverse Event Review

Protocol-related AEs will be collected annually on the CRF from years 1-5. Any persisting, protocol-related adverse effects will be reported annually on the CRF from years 6-10. Serious Adverse Events (SAEs) will be reported from study entry until 5 years post-randomisation in accordance with Section 16 Adverse Event Reporting.

7.1.8 Survival

Sites should report patient deaths by completing the Death Form immediately upon being made aware of the event.

Page **19** of **48** Version 4.0, 15th March 2016

7.2 Active Monitoring Arm Patients

7.2.1 Baseline

Baseline data will be collected, to include details of all the diagnostic biopsy histology, details of current or planned endocrine therapy and data on any current Hormone Replacement Therapy (HRT), Non-steroidal anti-inflammatory drugs (NSAIDs) and biguanides.

7.2.2 Treatment

7.2.2.1 Surgery

Patients in the Active Monitoring arm will not undergo primary surgery.

7.2.2.2 Endocrine Therapy

The use of endocrine therapy is not mandated within the trial, however, data on the use of endocrine therapy will be captured on the CRF.

7.2.3 Annual Follow-up

Annual follow-up data will be obtained from an annual telephone call to the patient, until 10 years post-randomisation. Patients should be contacted within one month of attending for annual mammography or following completion of any investigations, if indicated.

Any planned additional follow-up for patients in the Active Monitoring arm will be in accordance with local guidelines.

7.2.3.1 Mammography

Patients must be invited to attend for annual mammography for 10 years. After 10 years, mammographic follow-up will be according to local guidelines; for the majority of patients this will be within the NHSBSP or within a compatible follow-up trial (see Section 7.4 Concurrent Studies).

Following annual mammography, patients should be informed of the outcome of the mammogram as soon as possible, ideally within 2 weeks of mammography being carried out. Participating sites which inform patients of the outcome of their mammography via letter, should do so using one of two site-specific result letters; Recall or Non-recall. The result letters will be generated by the site but must contain appropriate wording regarding the screening interval (i.e. one year rather than three years) and in the case of the Non-recall letter, the wording of the result of the mammogram must be carefully worded to ensure that this is conveyed to patients in a consistent and appropriate manor. The appropriate result letter should be sent to the patient and a copy of the letter should be sent to the patient's GP, unless systems are in place to allow the GP to access the outcome of the mammogram independently. It is anticipated that a copy of the letter will also be filed in the patients' medical notes.

If a patient fails to attend for a mammogram appointment, a second appointment should be sent. If the patient fails to attend the second appointment, the patient's GP should be contacted to ensure that the patients address is correct. If the address is correct, a letter will be sent to the patient and GP asking them to contact their research nurse. If a patient does not respond to this invitation, the patient should be contacted by telephone. The site research team must make every effort to ensure that patient contact details are up to date and that all changes of address occurring in the 5 years post-randomisation are notified to SHORE-C by completing the Change of Contact Details Form. Note that changes to patient address and telephone details will be maintained by SHORE-C only and should not be provided to the Trial Office.

7.2.3.2 Breast Screening Programme Invitation

Patients should be advised to contact the Research Team at their randomising hospital if they receive an invitation to attend for a mammogram through the NHS Breast Screening Programme. Patients do not need to attend for these additional appointments and should be advised not to.

7.2.3.3 Ipsilateral Mammographic Indications for Patient Recall

An increase in the number, or size, of the microcalcification in the index lesion should not prompt routine patient recall. Neither should changes in the appearances/morphology, as casting type microcalcification is known to become more prevalent with increasing size.

Mammographic changes that would warrant a recall to clinic for further investigations are:

- A new cluster of microcalcification which is not definitively benign, outwith the index lesion/quadrant or remote from the index lesion
- A new cluster of microcalcification, which is not definitively benign in the contralateral breast
- A new non-calcified lesion which is not definitively benign in either breast
- Developing asymmetry or mass around the index calcification

7.2.4 Radiological Second Opinion Service

When a radiological second opinion is required, the current images and any prior images (if not previously captured) will be locally anonymised and uploaded for review via Image Exchange Portal or the local equivalent, to enable the images to be reviewed via an NHS computer. Participating sites which are unable to transfer images in this way should submit anonymised images for review on CD via post, including the patient's TNO, date of birth and date of mammogram only as identifiers. A request for the radiology second opinion service should be emailed to the Trial Office.

The outcome of the radiology review will be notified via email to the main contact, reporting radiologist, nominated lead radiologist and Principal Investigator within 7 days of the images being uploaded.

7.2.5 Investigations and Treatment of Ipsilateral Breast Disease

Please see Flowchart 2: Investigation Algorithm, later in this section.

Investigational biopsies will be taken in the Active Monitoring arm patients, as deemed appropriate by the site research team. In the case of suspected new disease in the ipsilateral breast, the histology slides will be submitted to the Trial Office for Central Histopathology Review (as for the diagnostic slides pre-study entry), in accordance with the LORIS Pathology and Sample Collection Guidelines.

The outcome of the Central Histopathology Review will be reported as either continue Active Monitoring or discontinue Active Monitoring. If there is no change in DCIS morphology, or the patient is confirmed to have additional low risk DCIS or benign disease, the patient will continue with Active Monitoring. If DCIS other than low risk or if invasive disease is confirmed, the patient will discontinue Active Monitoring and should be treated according to local protocol.

The outcome of the Central Histopathology Review will be notified via email to the main contact, reporting pathologist and nominated lead pathologist within 7 days of the slides being received by the Trial Office.

Details of all investigations (regardless of outcome) and subsequent treatment will be collected on the CRF.

7.2.6 Investigations and Treatment of Contralateral Breast Disease

Suspected new disease in the contralateral breast should be investigated and treated according to local protocol. Details on confirmed disease in the contralateral breast will be collected.

7.2.7 Data Capture

Data on the outcome of annual mammography, related referrals to other healthcare practitioners, all related investigations (regardless of outcome), disease progression or development of new breast disease and related treatment will be collected on the CRF.

Further details on progression of disease beyond that of the entry criteria, development of new breast disease and development of first related distant metastases will be reported on the appropriate CRF.

7.2.8 Related Adverse Event Review

Protocol-related AEs will be collected annually on the CRF from years 1-5. Any persisting, protocol-related adverse effects will be reported annually on the CRF from years 6-10. SAEs will be reported from study entry until 5 years-post randomisation in accordance with Section 16 Adverse Event Reporting.

Page **21** of **48** Version 4.0, 15th March 2016

[figure not shown]
7.2.9 Survival

Sites should report patient deaths by completing the Death Form immediately upon being made aware of the event.

Page **22** of **48** Version 4.0, 15th March 2016

7.2.10 Flowchart 2: Investigation Algorithm

Page **23** of **48** Version 4.0, 15th March 2016

7.3 Protocol Deviations and Patient Withdrawal

7.3.1 Protocol Deviations

The details of the protocol deviation (date, reason and type of deviation) should be clearly documented in the source data. A Deviation Form should be completed to notify the LORIS Trial Office of the deviation. Patients will continue to be followed-up on an intent-to-treat basis.

7.3.2 Withdrawal of Consent

Patients may withdraw consent at any time during the trial. For the purposes of this trial, three different types of withdrawal are defined:

- The patient would like to withdraw from the randomised allocation, but is willing to be followed up according with the schedule of assessments (i.e. the patient has agreed that data can be collected and used in the trial analysis)
- The patient would like to withdraw from the randomised allocation and does not wish to undergo study assessments in accordance with the schedule of events but is willing to be followed up at standard clinic visits (i.e. the patient has agreed that data can be collected at standard clinic visits and used in the trial analysis)
- The patient would like to withdraw from the randomised allocation and is not willing to be followed-up for the purposes of the trial at any further visits (i.e. only data collected prior to the withdrawal of consent can be used in the trial analysis)

The details of withdrawal (date, reason and type of withdrawal) should be clearly documented in the source data. A Withdrawal of Consent Form should be completed to notify the LORIS Trial Office of the patient's withdrawal.

7.4 Concurrent Studies

Investigators wishing to enrol patients into another trial should contact the LORIS Trial Office in the first instance. The LORIS Trial Management Group (TMG) will consider the enrolment of LORIS patients into other trials that do not interfere with the analysis of the primary outcome or introduce bias. Examples include trials of imaging, supportive treatment and adjuvant radiotherapy.

Page **24** of **48** Version 4.0, 15th March 2016

8 QUALITY OF LIFE

8.1 Quality of Life

The primary QoL aspect of the trial examines the hypothesis that the psychological well-being of women in the Active Monitoring arm is non-inferior to that associated with standard surgical and adjuvant treatments. In addition, these QoL outcomes will inform future patients diagnosed with low risk DCIS when making decisions about their treatment options. Patients will be asked to complete questionnaires at different time points (see Table 1 Timeline of Quality of Life Questionnaires, later in this section) that will look at factors that may influence:

- Decision to join or reject the trial using the Accept/Decline questionnaire (Feasibility Study only)
- Psychological adjustment anxiety trait and ways of coping. Using the Speilberger State-Trait Anxiety Inventory (STAI) and Brief ways of coping questionnaire (baseline only)

In addition, the impact that either Surgery or Active Monitoring may have on anxiety state and general well-being is measured using:-

- STAI
- SF-36v2 Health Survey

8.1.1 Accept/Decline Questionnaire

During the Feasibility Study, women who are offered participation in the trial will be invited to complete an Accept/Decline questionnaire. The questionnaire initially asks patients if they have agreed or not to trial entry. Patients then rate on a 5-point Likert scale to what extent they agree or disagree with a list of 19 reasons that might influence their decisions. This questionnaire has been employed in several research studies examining entry into randomised clinical trials (45) including the on-going PulMiCC (Pulmonary Metatastectomy in Colorectal Cancer) trial.

8.1.2 Brief COPE Questionnaire

The Brief Ways of Coping Questionnaire (46) assesses how individuals cope with stressful situations via problem-solving and emotion-regulation. Participants will indicate whether they "have been doing this a lot", "doing this a medium amount", "doing this a little", "haven't been doing this" in respect to 28 questions.

8.1.3 State-Trait Anxiety Inventory

The STAI consists of 2 questionnaires with 20 items, each rated on simple 4 point scales. It is a well-known, validated research clinical tool for evaluating anxiety proneness (Trait) and the current state of anxiety or anxiety change (State). It is self-administered and has been used successfully in many breast cancer studies.

8.1.4 SF-36v2 Health Survey

The SF-36v2 Health Survey is a 36-item instrument for measuring Health-Related QoL (HRQoL) in a general population via patient self-report. The SF-36v2 measures the following eight health concepts, which are relevant across age, disease, and treatment groups: physical functioning, role limitations due to physical health problems, bodily pain, general health, vitality (energy/fatigue), social functioning, role limitations due to emotional problems, and mental health (psychological distress and psychological well-being).

8.1.5 Euro Qol EQ-5D (EQ-5D)

The EQ-5D is a health status measure comprised of 5 attributes or dimensions; mobility, self-care, usual activity, pain/discomfort, and anxiety/depression. The single summary scores derived from the EQ-5D will be used in QALY analyses and in cost-effectiveness and cost-utility analyses.

Page **25** of **48** Version 4.0, 15th March 2016

Table 1. Timeline for Quality of Life Questionnaires

	Time points (months)							
Questionnaire	Baseline	3	6	12	24	36	48	60
Accept/Decline (Feasibility Study only)	х							
Brief COPE	х							
STAI Trait Anxiety	Х							
STAI State Anxiety	Х	Х	Х	Х	Х	Х	Х	Х
SF-36v2 Health Survey	Х	Х	Х	Х	Х	Х	Х	Х
EuroQol EQ-5D	Х	Х	Х	Х	Х	Х	Х	Х

With the exception of the baseline QoL questionnaires that are completed by the patient prior to randomisation, all other questionnaires will be distributed directly to the patients' home address by SHORE-C, for completion at the designated time points. A member of the SHORE-C team may contact the patient if the questionnaires that have not been returned or have not been completed fully.

The site research team should inform SHORE-C of any changes to the patients address or telephone number by completing the Change of Contact Details Form. Note that changes to patient address and telephone details will be maintained by SHORE-C only and should not be provided to the Trial Office.

8.2 Patient Telephone Interviews

During the Feasibility Study, a proportion of women (12-15) will take part in a telephone interview with a researcher from SHORE-C. These interviews will explore the usefulness of the trial information (Patient Information Sheet and Patient Information DVD) supplied, their thoughts on the LORIS study and which aspects of the study influenced their decision to participate or not. A small proportion of women may refuse their randomised allocation; it would be helpful to interview these women also. It is important that both women who accept or decline LORIS study entry are interviewed.

9 HEALTH ECONOMICS

9.1 Form of the Health Economic Evaluation

If Active Monitoring is found to be an effective approach in the treatment for confirmed low risk DCIS then it is likely that there will be important cost implications for the health care sector. For example, the patient will avoid initial standard surgery and adjuvant treatment (according to local protocol) and will instead be monitored by annual mammography and be treated as an outpatient, thus avoiding an inpatient stay and resources may be saved. However, active monitoring may, or may not, incur unexpected or unscheduled costs due to additional appointments for reassurance using health care resources for example in providing counselling between mammography screens. Therefore all associated resource use costs incurred by both approaches need to be assessed in conjunction with measures of effectiveness.

The aim of the economic evaluation is to determine the cost-effectiveness of active monitoring compared with surgery and adjuvant therapy for low risk DCIS. Although the trial has been designed as a non-inferiority trial, the most appropriate type of analysis is a cost-effectiveness analysis (47). Cost-effectiveness will be determined in two ways: a cost-effectiveness analysis will be undertaken based on a number of outcomes including the cost per additional surgical treatment avoided at 10 years and cost per diagnosis of ipsilateral breast cancer, utilising the clinical outcome data collected within the trial. In addition, a cost-utility analysis will be undertaken to calculate the cost per additional quality-adjusted life year (QALY) gained. The utility values required to calculate QALYs will be obtained by administering the EuroQol EQ-5D questionnaire at the time points described in Section 11.1. In the first instance, the evaluation will consider costs incurred by the health service in the delivery of both treatment pathways. However, information on costs incurred by patients will also be collected in order that an evaluation from a wider societal perspective can also be undertaken.

Page **26** of **48** Version 4.0, 15th March 2016

9.2 Cost Data Collection

Data collection will be undertaken prospectively for all trial patients so that a stochastic cost analysis can be undertaken. The process of collecting resource use data will be undertaken separately from data collection on unit costs.

The main resource uses to be monitored from the trial by the site research team (but not directly from the patients) include the following:

- Consultation time required to explain each procedure for explanation and consent
- Surgical procedures (identification of procedures will be collected as part of the trial data collection; resource use associated with procedures will be collected from time and motion study where appropriate or staff / expert opinion)
- Adjuvant therapy (which is provided according to local protocol and will differ across sites). This data
 will be captured by a survey of protocols from the range of sites and the full range will be tested in the
 probabilistic sensitivity analysis
- Resource use involved with mammography procedures (from a staff survey questionnaire or experts and/or (compared with) HRG cost data for mammography)
- Costs involved with other related procedures, including level of health care professional involvement in the procedure, equipment required, overheads, consumables and drugs including anaesthesia
- Any additional procedures required where initial treatment is unsuccessful or incomplete
- Duration of inpatient stay for the surgical procedure

Information on additional related primary or secondary care contacts will also be collected from women to ensure any resulting resource use from additional complications is recorded. The best approach to this data collection is likely to be the cross sectional approach to investigate community based healthcare and participant resource use for the first 5 years post randomisation and follows that used by the ProtecT Trial.

A Patient Costs Questionnaire is used to collect patient data, on private travel for hospital appointments and time off work for example, with the aim of obtaining cross-sectional community based healthcare and participant resource use for the first 5 years post randomisation. However, to achieve this, a specific resource use questionnaire is distributed to all women at one time point. In the Feasibility Study, the questionnaire will be distributed to women 2 years after the first woman is randomised. This approach will capture some women at 24 months post randomisation, some at 20, 19, 18 12, 6 months etc., for a number of different time points, depending when randomised. The approach can be used to ensure that no woman receives more than one questionnaire. The questionnaires will be designed to ask women about their resource use in the previous 4 months. In the main trial (24-60 months) questionnaires will again be administered to women at a single time point (excluding those who participated during the feasibility phase) and participants will be asked about resource use in the previous 6 months. The questionnaire will contain questions to determine out of pocket expenses incurred (e.g. transport costs) when attending for treatment and private time costs including time lost from work. This approach would capture specific resource use for all women randomised into the study for complete coverage of five years. This approach follows the success of capturing the analogous data for men in the NIHR-HTA funded ProtecT Trial and CAP studies currently in progress for prostate cancer. Unit costs will be obtained and attached to resource items in order that a cost can be calculated for each trial patient. Published sources for these costs will include Unit Costs of Health and Social Care (48) and NHS Reference costs. Also some primary cost data will be collected from a representative sample of participating hospitals.

Participants will be sent the Patient Costs Questionnaire by post directly to their home address by SHORE-C

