16.1.5 Specific Progression Criteria from Feasibility Study to Main Trial

- 20 sites trained, open and recruiting by the end of year 2
- 60 patients randomised by the end of year 2
- · Mean monthly recruitment of at least 6 patients in the last 4 months, as defined above

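### The feasibility Patient Costs Questionnaire looks back a fixed 4 months, not limited to time since randomisation, and recently randomised women are not asked again

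*Protocol*

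**What the plan says.** Protocol section 9.2 (Cost Data Collection) sets the rules for the Patient Costs Questionnaire:

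- **Target.** The questionnaire is used "with the aim of obtaining cross-sectional community based healthcare and participant resource use for the first 5 years post randomisation".
- **Recipients.** To achieve this, "a specific resource use questionnaire is distributed to all women at one time point".
- **Date.** "In the Feasibility Study, the questionnaire will be distributed to women 2 years after the first woman is randomised".
- **Time since randomisation.** "This approach will capture some women at 24 months post randomisation, some at 20, 19, 18 12, 6 months etc". The list is open-ended and gives no lower limit.
- **Recall.** "The questionnaires will be designed to ask women about their resource use in the previous 4 months".
- **One per woman.** "The approach can be used to ensure that no woman receives more than one questionnaire". The main-trial round, with a 6-month recall, is sent "excluding those who participated during the feasibility phase".

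Section 16.1.5 requires 60 women randomised by the end of year 2 and "Mean monthly recruitment of at least 6 patients in the last 4 months". Randomisation is therefore still running, probably at its fastest, when the feasibility mailing goes out.

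**The concern.** The recall period and the target period do not match. A woman randomised t months before the mailing, with t below 4, has only t months of post-randomisation time in her window. The other 4 − t months come before allocation. Section 6.1.1 allows up to 90 days between diagnosis and registration, so visits, travel and time off work for biopsy and assessment can fall in that part.

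She is not surveyed again, so the post-randomisation months missing from her window are not recovered. Section 7.1.2.1 expects surgery within 60 days of randomisation. Some Surgery arm women may therefore be asked before their operation and never report the travel, recovery time or community care that follow it.

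At stake are the level of patient-reported cost in the first months and, depending on the denominator used, the early difference between arms.

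**Working it through.** The protocol gives no figure of its own to reproduce. The check is arithmetic on its stated rules.

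**Inputs.** Mailing at month 24 and 4-month recall (section 9.2); 60 women, with at least 6 per month in the last 4 months (section 16.1.5); 932 women in total (section 16).

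**Assumptions.** Entry is even within the last 4 months. The 24 months of the Feasibility Study and the 2 years from first randomisation are treated as the same clock.

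**1. Women whose window opens before randomisation.** Number = 4 × m, where m is monthly recruitment in the last 4 months. On average 2 of their 4 recalled months are pre-randomisation. Total recalled time is 60 × 4 = 240 woman-months.

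| Recruitment in last 4 months | Women affected | Pre-randomisation woman-months | Share of 932 |
|---|---|---|---|
| 6 per month (criterion minimum) | 24/60 = 40% | 48/240 = 20% | 2.6% |
| 60/24 = 2.5 per month (even accrual) | 10/60 = 17% | 20/240 = 8% | 1.1% |
| 8 per month (illustrative, above the minimum) | 32/60 = 53% | 64/240 = 27% | 3.4% |

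For a single woman, taking 4 months as 121.75 days: randomised 7 days before mailing, (121.75 − 7)/121.75 = 94% of her window is pre-randomisation; at 60 days, 51%. At 6 per month, 2 × 6 = 12 women are mailed within about 2 months of randomisation.

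**2. How much of the early feasibility data comes from these women.** At the criterion minimum, spread the other 36 women evenly over the first 20 months (1.8 per month).

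- Months 0–4 after randomisation: affected women give 6 × 8 = 48 woman-months. Women mailed at 4–8 months give 1.8 × 8 = 14.4. Share = 48/62.4 = 77%.
- Months 0–2: affected women give 6 × 6 = 36. Women mailed at 4–6 months give 1.8 × 2 = 3.6. Share = 36/39.6 = 91%.
- With constant accrual r, the shares are 8r/16r = 50% and 6r/8r = 75%.

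**3. Effect on the difference between arms.** Let the true difference be d per month after randomisation, and let pre-randomisation costs be equal in expectation. If each woman's total is divided by 4 months, the expected difference is d × t/4. Averaged over t from 0 to 4, this is d/2, so the early difference in this group is halved. If the denominator is actual post-randomisation months, the absolute difference is not attenuated, but pre-randomisation costs still inflate the level in both arms unless they are removed.

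**4. What excluding recent women would do.** With constant accrual r, dropping women under 4 months from randomisation cuts feasibility coverage of months 0–2 from 8r to 2r woman-months (−75%) and of months 0–4 from 16r to 8r (−50%).

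**The case against.** A reader might infer that pre-randomisation diagnostic costs are carried into the comparison of arms and bias it. The documents do not support that.

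- No section states such an analysis rule. Section 16.2.2 makes the feasibility evaluation model-based only, and the within-trial analysis comes when 75% of patients have reached 5 years.
- Under 1:1 randomisation, costs before allocation are equal in expectation. They cancel in the absolute difference and add noise. Attenuation needs the extra step of using 4 months as the exposure denominator, which the protocol does not prescribe.
- Surgical procedures, adjuvant therapy and inpatient stay are collected through sites (section 9.2), not from this form. Section 9.1 takes the health service perspective first; patient costs serve the wider societal one.
- The design is cross-sectional, so each woman is meant to give only one short snapshot. A short contribution from one woman is not in itself a fault.
- The affected women are about 2.6% of 932.

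All of this stands, and it keeps the point small. It does not remove it. The recall period is a collection rule. Costs could be cut at randomisation afterwards only if the items are dated, and the protocol does not say that they are. The comparison with 932 also understates the weight of these women in the feasibility data on the first months. Section 16.2.2 gives the feasibility evaluation the purpose of checking that the right data are being collected, so this is a fitting place to settle the wording.

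**Conclusion.** The point holds as a minor mismatch between the recall rule in section 9.2 and its stated target. At the progression minimum it affects 24 of 60 feasibility women (40%) and about 20% of recalled woman-months. Even accrual gives 17% and 8%; 8 per month gives 53% and 27%. These women supply half or more of the feasibility data on months 0–4, and at least three quarters on months 0–2, under the criterion-minimum and even-accrual patterns. Their early difference between arms is roughly halved only if 4 months is the denominator.

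The result rests on even entry within the last 4 months, on the two clocks agreeing, and, for the halving, on a constant monthly difference. It concerns patient-reported travel, time and community costs. It does not show a biased arm comparison. Whether the 6-month recall repeats the problem depends on whether the 24–60 months given for the main-trial round means time since randomisation or trial time, which section 9.2 leaves unclear; no size is claimed for that round.

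**What to change.** In section 9.2, word the question as *in the last 4 months, or since you joined the study if that is shorter*, and state that costs are divided by each woman's actual post-randomisation months in the window. Use the same wording with 6 months in the main-trial round for any woman mailed within 6 months of randomisation.

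Do not leave recently randomised women out of the mailing. That would discard the early-month coverage shown in step 4, and a later 6-month recall may not reach back to those months.

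The cost is one question stem and one sentence of protocol text. The downside is a somewhat shorter recall for some women and an exposure denominator that varies between women. If the feasibility mailing has already gone out, the wording can still be used in the main round. For forms already returned, the new denominator is fully right only where pre-randomisation items can be identified and removed.
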